#### 9.1.2 Serious Adverse Events

Investigators should report AEs that meet the definition of an SAE (see Appendix 3 for definition).

#### 9.1.2.1 Monitoring pregnancies for potential Serious Adverse Events

If a patient becomes pregnant on study selumetinib should be discontinued. It is important to monitor the outcome of pregnancies in order to provide SAE data on congenital anomalies or birth defects.

If a patient or their partner becomes pregnant during the SAE reporting period please complete a Pregnancy Notification Form (providing the patient's details) and return to the Trial Office within 30 days. If it is the patient who is pregnant provide outcome data on a follow-up Pregnancy Notification Form. Where the patient's partner is pregnant consent must first be obtained and the patient should be given a Release of Medical Information Form to give to their partner. If the partner is happy to provide information on the outcome of their pregnancy they should sign the Release of Medical Information Form. Once consent has been obtained provide details of the outcome of the pregnancy on a follow-up Pregnancy Notification Form. If appropriate also complete an SAE Form as detailed below.

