# 4 ELIGIBILITY

### 4.1 Inclusion Criteria

- HIV positive and established on a HAART regimen for ≥ 3 months.
- · Histologically confirmed KS
- Measurable disease according to ACTG criteria.
- Progressive cutaneous or nodal KS not requiring chemotherapy OR progressive KS following cytotoxic chemotherapy.
- Evidence of disease progression in the past 6 months. No anti-cancer treatment within one month prior to commencing trial treatment.
- Adequate haematological function:
  - o Haemoglobin ≥ 9 g/dL
  - Absolute neutrophil count ≥ 1.5 x 10^9/L
  - o Platelets ≥ 100 x 10^9/L
- Adequate hepatic function:
  - Serum bilirubin ≤ 1.5 x upper limit of normal (ULN), except if the patient is established on the anti-retroviral drug atazanavir (no upper limit) and has AST and ALT levels ≤ 2.5 x ULN
  - ALT ≤ 2.5 x ULN
  - o AST ≤ 2.5 x ULN
- Adequate renal function:
  - o Serum creatinine clearance > 50 ml/min (Cockcroft-Gault formula or 24 hour urine collection).
- Age ≥ 18 years.
- World Health Organisation (WHO) performance status ≤ 2.
- For selumetinib, women of child bearing age and child bearing potential MUST have a negative
  pregnancy test prior to study entry AND be using an adequate contraception method, which must
  be continued while on treatment and for at least 4 weeks after the study treatment has ended.
- Male patients must agree to use an effective contraception method while on treatment and for at least 16 weeks after the study treatment has ended (barrier contraception is recommended for all individuals living with HIV).
- Written informed consent.

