- Reproductive toxicology data indicate that selumetinib has adverse effects on embryofoetal development and survival at dose levels that do not induce maternal toxicity in mice. Subsequently, selumetinib should not be administered to pregnant or breast-feeding women and conception while on treatment must be avoided. Female patients of child-bearing potential will be required to use reliable methods of contraception for the duration of the study and until 4 weeks after the last dose of selumetinib. Male patients with sexual partners who are pregnant or who could become pregnant (i.e. women of child-bearing potential) should use acceptable methods of contraception for 16 weeks after completing the study to avoid pregnancy and/or potential adverse effects on the developing embryo. In any case barrier contraception is recommended for individuals living with HIV.

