#### 9.1.3 Reporting period

Details of all AEs will be documented and reported from the date of commencement of protocol defined treatment until 30 days after the last administration of selumetinib.

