Post Treatment Adverse Event Follow-Up Form	Record AEs that have not resolved to baseline at 30 Day Post-Discontinuation visit.	Within 2 weeks.
Pregnancy Notification Form.	Record pregnancy of patient or patient's partner	Immediately upon notification of pregnancy.
Treatment Discontinuation Form.	Date and reason for discontinuation.	Within 1 week.
Death Form.	Date and cause of death.	Immediately upon notification of patient's death.
Withdrawal Form.	thdrawal Form. Date and reason for patient withdrawal.	
Deviation Form.	Completed in the event of deviation from the protocol.	Immediately upon discovering deviation.
Cycle 1 Forms		
Copy of Adverse Events Form *	List of all adverse events.	End of Cycle 1. Within 1 week
Copy of Concomitant Medications Form *	List of concomitant medication.	End of Cycle 1. Within 1 week

\*Adverse Events Form and Concomitant Medications Form must be photocopied and sent to the Trial Office within 1 week of the End of Cycle 1 (Cycle 1 Day 22 visit).

The CRF must be completed, signed/dated and returned to the Trial Office by the Investigator or an authorised member of the site research team (as delegated on the Site Signature and Delegation Log) within the timeframe listed above.

Entries on the CRF should be made in ballpoint pen, in blue or black ink, and must be legible. Any errors should be crossed out with a single stroke, the correction inserted and the change initialled and dated. If it is not obvious why a change has been made, an explanation should be written next to the change. Data reported on each form should be consistent with the source data or the discrepancies should be explained. If information is not known, this must be clearly indicated on the form. All missing and ambiguous data will be queried. All sections are to be completed before returning.

In all cases it remains the responsibility of the Investigator to ensure that the CRF has been completed correctly and that the data are accurate. The completed originals should be sent to the Trial Office and a copy filed in the ISF. Trial forms may be amended by the Trial Office, as appropriate, throughout the duration of the trial. Whilst this will not constitute a protocol amendment, new versions of the form must be implemented by participating sites immediately on receipt.

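### Pregnancy notification stops being required 30 days after the last dose, while male patients' contraception period runs for at least 16 weeks after treatment

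*Protocol*

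**What the plan says.** **Contraception period, men.** Protocol section 4.1 (Inclusion Criteria): "Male patients must agree to use an effective contraception method while on treatment and for at least 16 weeks after the study treatment has ended". Section 7.3.1 repeats the 16 weeks for men whose partners are or could become pregnant, but counts them from a different point: "for 16 weeks after completing the study to avoid pregnancy and/or potential adverse effects on the developing embryo".

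**Contraception period, women.** Section 7.3.1: "for the duration of the study and until 4 weeks after the last dose of selumetinib". Section 4.1 also gives at least 4 weeks.

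**When a pregnancy must be notified.** Section 9.1.2.1: "If a patient or their partner becomes pregnant during the SAE reporting period please complete a Pregnancy Notification Form". The same section gives the purpose, which is to obtain SAE data on congenital anomalies and birth defects. It already provides for outcome data on a follow-up form, subject to consent where the partner is the one who is pregnant.

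**When the reporting period ends.** Section 9.1.3 runs it from the start of protocol treatment "until 30 days after the last administration of selumetinib". Section 7.9.4 also marks the 30-day post-discontinuation visit as its end. The protocol defines no separate SAE period.

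**When the form is due.** Section 9.1.2.1 allows 30 days for its return. The table in section 10.1 says "Immediately upon notification of pregnancy" and sets no limit on when the pregnancy began.

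**The concern.** The two rules serve the same purpose but end at different times. Section 7.3.1 explains male contraception partly by possible harm to an embryo, and section 9.1.2.1 explains notification by the need to learn of congenital anomalies. Yet the duty to notify lapses well before the contraception period ends.

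At stake is a safety signal, not an efficacy result. Appendix 3 makes a congenital anomaly an SAE, but an anomaly would be recognised long after routine reporting has closed under 9.1.3. The Pregnancy Notification Form is the protocol's explicit route by which such an outcome becomes SAE data. It is then passed to the manufacturer under 9.2.4. If the first form is not required, nothing obliges the site to start that chain.

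**Working it through.** The protocol states no figure for this gap, so there is none to reproduce. The check is day arithmetic, taking the end of treatment as the day of the last dose.

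**Inputs**
- Male contraception after treatment: 16 weeks (4.1), 16 × 7 = 112 days, stated as a minimum.
- Female contraception after treatment: 4 weeks (4.1, 7.3.1), 4 × 7 = 28 days.
- Notification after the last dose: 30 days (9.1.2.1 read with 9.1.3).
- Standard treatment: six cycles of 21 days (7.2), 6 × 21 = 126 days.

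**Post-treatment gap**
- Men: 112 − 30 = 82 days, which are days 31 to 112. Share: 82/112 = 73%.
- Women: 28 < 30, so no gap.

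**Share of the whole male contraception period.** With T days of treatment, all inside the reporting period, the uncovered share is 82/(T + 112).

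| Treatment | T (days) | Uncovered share |
|---|---|---|
| One cycle | 21 | 82/133 = 62% |
| Two cycles | 42 | 82/154 = 53% |
| Six cycles | 126 | 82/238 = 34% |
| One year | 365 | 82/477 = 17% |

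The share exceeds one half only if T + 112 < 164, that is, if treatment lasts less than 52 days. The number of uncovered days stays at 82 throughout.

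**Start of the 16 weeks.** Section 4.1 counts from the end of treatment and section 7.3.1 from completing the study. If completing the study means the end of the 12-month follow-up in 7.11 (an assumption, since 7.3.1 does not say), the period ends on day 365 + 112 = 477 and the gap is 477 − 30 = 447 days. So 82 days is the smaller of the two readings.

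**Which follow-up visits could pick this up.** Visits are every 12 weeks, give or take 7 days (7.9.6, 7.11). Counted from the end of treatment, the first falls at about day 84, which is 28 days before day 112. It cannot ask about days 85 to 112 and may come too early for a recent conception to be known. The second falls at about day 168, which is 56 days after day 112. Both are needed.

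**The case against.** Several points on the other side are sound.

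- **A reader might infer that these pregnancies are never captured, or that the trial cannot detect them.** The protocol does not support that. Section 9.1.2.1 says when a form is required and does not bar later ones. The 10.1 table lists the form for a pregnancy of the patient or partner with no time window, and 7.11 keeps patients in follow-up for 12 months. A site can learn of a later pregnancy and report it. What stands is that it need not.
- **A reader might infer that most of the risk window is uncovered.** That holds for the post-treatment part (73%). Under 4.1 the contraception period also includes time on treatment, which is covered, and the share after six cycles is 34%.
- **A reader might infer that days 31 to 112 carry an established hazard.** The animal finding in 7.3.1 concerns embryofoetal effects at doses not toxic to the mother. The protocol gives no data on paternal exposure, and a contraception period is a precaution. The gap is between two of the protocol's own rules and does not demonstrate risk.
- **Few events are likely.** The trial expects 12 phase I and 25 phase II patients, with those treated at the recommended dose counted in both, and contraception is an entry condition. No endpoint or decision rule is affected. This limits the weight of the point, but with so few patients each pregnancy outcome also carries more information.
- **Other instructions may exist.** Section 9.2.1.2 refers sites to SAE form guidelines in the site file, which are not shown. They might ask for more, but the protocol text should not depend on that.
- **The deadline conflict is separate.** It is editorial and does not bear on the gap.

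**Conclusion.** The mismatch is real and should be corrected. As written, the protocol does not require notification of a partner pregnancy that begins on days 31 to 112 after treatment: 82 of 112 post-treatment days (73%), or 34% of the full contraception period after six cycles. Female patients are unaffected.

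This rests on three assumptions: that the SAE reporting period in 9.1.2.1 is the period defined in 9.1.3, the only one given; that the 16 weeks run from the last dose, as in 4.1; and that no instruction outside the protocol extends the duty. The 7.3.1 start point would lengthen the gap. The conclusion is limited to what is required. It does not say that such pregnancies would go unseen or that harm is expected.

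**What to change.** **Change to 9.1.2.1.** Replace the SAE reporting period as the trigger with the period from the start of treatment to the end of the contraception period that the protocol itself sets, for the patient or the partner as applicable. The existing outcome follow-up and consent steps can stay as they are.

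**Prompt.** Ask about pregnancy at the 12-week follow-up contact and at the one after it. Section 7.9.6 ends physical examinations at progression while 7.11 follows all patients for 12 months, so the amendment should state that the question is also put to patients who have progressed.

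**Reconcile in the same amendment**
- The start of the 16 weeks: "while on treatment and for at least 16 weeks after the study treatment has ended" in 4.1 against "for 16 weeks after completing the study to avoid pregnancy and/or potential adverse effects on the developing embryo" in 7.3.1. The sponsor should settle which is meant and use it in both places and in the trigger. If it is the later one, the timing of the follow-up question needs to be revisited.
- The form deadline: the 30 days in 9.1.2.1 against "Immediately upon notification of pregnancy" in 10.1.

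**Cost.** A short text amendment and one question at two contacts, using a form and a follow-up schedule that already exist. It changes reporting only and leaves dose, contraception duration and clinical management untouched. The downside is an occasional extra notification.

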#### 9.1.3 Reporting period

Details of all AEs will be documented and reported from the date of commencement of protocol defined treatment until 30 days after the last administration of selumetinib.

# 9.2 Reporting Procedure

#### 9.2.1 Site

#### 9.2.1.1 Adverse Events

AEs should be reported on an AE Form (and where applicable on an SAE Form). An AE Form should be completed at each visit and returned to the Trial Office. AEs will be reviewed using the Common Terminology Criteria for Adverse Events (CTCAE), version 4.0 (see Appendix 4). Any AEs experienced by the patient but not included in the CTCAE should be graded by an Investigator and recorded on the AE Form using a scale of (1) mild, (2) moderate or (3) severe. For each sign/symptom, the highest grade

observed since the last visit should be recorded. When an adverse event changes CTCAE grade it should be recorded as an individual AE.

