# 7.4 Dose Modifications

Selumetinib doses will be adjusted for haematological and other adverse events considered at least partly due to administration of selumetinib in combination with HAART. Dose adjustments are to be made according to the greatest degree of toxicity. Adverse events will be graded using the CTCAE (see Appendix 4). Dose escalation outside of the dose finding study in phase I is not permitted.

The guidelines which follow outline dose adjustments for several of these toxic effects. If a patient experiences several adverse events and there are conflicting recommendations, please use the recommended dose adjustment that reduces the dose to the lowest level.

Treatment with selumetinib should be withheld if one of the following toxicities considered related to treatment with selumetinib are observed, despite optimal supportive care:

- · Any intolerable adverse event regardless of grade
- Any adverse event CTCAE grade ≥ 3 (should be reported as a DLT, see section 3.1.1 for definition).

In the event of a DLT, report to the SCART Trial office within 24 hours of the investigator becoming aware of the event, via phone or email **[name] or [name]** 

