# 7.4.2 Non-Haematologic Adverse Events (including biochemistry/hepatic/renal function)

Grade of	Management/Next Dose for Selumetinib							
Event								
grade 1	no change in dose							
grade 2	Hold until ≤ grade 1∞ – resume at same dose, except for rash where							
	CTCAE grade 2 rash is acceptable							
grade 3	Hold* until < grade 2 – resume at 1 dose level lower if indicated,**							
	except for rash where patients with CTCAE grade 2 rash may restart							
	treatment (unless defined as a DLT).							
grade 4	Off protocol therapy							
								

- \* Patients requiring a delay of > 2 weeks should go off protocol therapy.
- \*\* Patients requiring > 2 dose reductions should go off protocol therapy.
- ∞Please refer to Appendix 10 for management of elevated creatine kinase

7.5 The dose modification algorithm allows for the following dose reductions:

75mg bd  $\rightarrow$  50mg bd  $\rightarrow$  75mg od

returns will be disposed of by Pharmacy according to local hospital practice. Further information can be found in the Pharmacy Manual (supplied separately).

CRCTU

Treatr

at the

es

ug

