#### 9.2.1.2 Serious Adverse Events

For more detailed instructions on SAE reporting refer to the SAE Form Completion Guidelines contained in section 5 of the Investigator Site File (ISF). AEs defined as serious and which require reporting as an SAE should be reported on an SAE Form. When completing the form, the Investigator will be asked to define the causality and the severity of the AE which should be documented using the CTCAE version 4.0. On becoming aware that a patient has experienced an SAE, the Investigator (or delegate) must complete, date and sign an SAE Form. The form should be faxed together with a SAE Fax Cover Sheet to the Trial Office using one of the numbers listed below as soon as possible and no later than 24 hours after first becoming aware of the event:

To report an SAE, fax the SAE Form with an SAE Fax Cover Sheet to: [name] or [name]

On receipt the Trial Office will allocate each SAE a unique reference number. This number will be transcribed onto the SAE Fax Cover Sheet which will then be faxed back to the site as proof of receipt. If confirmation of receipt is not received within 1 working day please contact the Trial Office. The SAE reference number should be quoted on all correspondence and follow-up reports regarding the SAE. The SAE Fax Cover Sheet completed by the Trial Office should be filed with the SAE Form in the ISF. For SAE Forms completed by someone other than the Investigator the Investigator will be required to countersign the original SAE Form to confirm agreement with the causality and severity assessments. The form should then be returned to the Trial Office in the post and a copy kept in the ISF. Investigators should also report SAEs to their own Trust in accordance with local practice.

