#### **Serious Adverse Event**

Any untoward medical occurrence or effect that at any dose:

- Results in death
- Is life-threatening\*
- Requires hospitalisation\*\* or prolongation of existing inpatients' hospitalisation
- Results in persistent or significant disability or incapacity
- · Is a congenital anomaly/birth defect
- Or is otherwise considered medically significant by the Investigator\*\*\*

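### Adverse events outside the CTCAE are graded only 1 to 3 on the AE Form, which conflicts with the SAE Form's severity scale and has no stated mapping to the grade-based dose rules

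*Protocol*

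**What the plan says.** Section 9.2.1.1 sets two grading systems for the AE Form. Events that the CTCAE covers are graded by CTCAE version 4.0. For events that it does not cover, the instruction is different: "graded by an Investigator and recorded on the AE Form using a scale of (1) mild, (2) moderate or (3) severe". The same section asks for the worst grade since the previous visit.

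Serious events follow a second route as well: "AEs should be reported on an AE Form (and where applicable on an SAE Form"). Section 9.2.1.2 then asks the investigator for causality and for "the severity of the AE which should be documented using the CTCAE version 4.0". It contains no provision for an event that the CTCAE does not list.

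Section 7.4, on dose modification, states: "Adverse events will be graded using the CTCAE (see Appendix 4"). The tables in 7.4.1 and 7.4.2 have separate rows for grades 3 and 4. Grade 3 leads to an interruption with a possible restart one dose level down. The grade 4 row reads "Off protocol therapy".

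**The concern.** The fallback scale mixes a three-level intensity rating with rules and forms that use CTCAE grades, and it has no code for a life-threatening or fatal event. Three things are at stake:

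- **The recorded grade.** A site that follows 9.2.1.1 exactly must enter 3 for the worst events in this class. A grade that was not collected at site cannot be reliably restored at analysis.
- **Agreement between forms.** The AE Form and the SAE Form are to be completed on different scales for one and the same event.
- **The dose rules.** Two rows of the dose-modification tables differ, and the protocol does not say which row an event rated 3 on the fallback scale belongs to.

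Toxicity of the combination is a secondary objective (2.1.2) and an outcome measure in both phases (2.2.2). Section 1.5.2 says that selumetinib has not been tested with HAART. Unanticipated events are therefore of particular interest, and an event outside a standard list could be one of them.

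**Working it through.** The protocol gives no figure for this point, so there is none to reproduce. The check sets the sections side by side and follows one hypothetical event through them: a life-threatening event, considered related to selumetinib, that the CTCAE does not list.

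1. **AE Form (9.2.1.1).** The event is outside the CTCAE, so the three-level scale applies. The highest available code is 3, and the worst-grade-since-last-visit rule cannot raise it. Recorded grade: 3.
2. **Is it also an SAE (Appendix 3)?** Yes. The definition lists life-threatening events and any event that "Results in death". An SAE Form is therefore required as well.
3. **SAE Form (9.2.1.2).** Severity is to be documented by CTCAE version 4.0. For a listed event the two forms use one scale. For an unlisted event, 9.2.1.1 prescribes the three-level scale and 9.2.1.2 prescribes the CTCAE. Either the investigator assigns a CTCAE-style grade by judgement, which may be 4 or 5 and so differ from the AE Form, or no valid entry exists. The protocol does not say which.
4. **Dose-modification tables (7.4 to 7.4.2).** These are entered by CTCAE grade. No text equates a fallback 3 with CTCAE grade 3, and no text says that the SAE Form severity governs instead. The row is undetermined, and the grade 3 and grade 4 rows differ.
5. **DLT definition (3.1.1.2).** The clause for other treatment-related effects treats grades 3 and 4 alike, so an event coded 3 counts just as one coded 4 would. The DLT count does not change. Phase I is in any case complete (3.1.2).
6. **Analysis (13.2.1, 13.2.2).** Toxicity per cycle is to be reported. No count or rate at grade 4 or above is defined. If a summary by grade were drawn from AE Form data, a life-threatening event in this class would appear one grade low (3 instead of 4) and a fatal event two grades low (3 instead of 5).

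For scale only, and on the assumption that such a summary gave a patient-level proportion over the 25 planned phase II patients, one patient so misclassified would shift it by 1/25 = 4 percentage points. The protocol does not specify that proportion, and it gives no basis for estimating how many patients would be affected.

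**The case against.** A reader might infer that a life-threatening or fatal event outside the CTCAE never reaches the grade 4 rule, or is lost to the safety record. The documents do not support that. Such an event is an SAE by definition and goes to the Trial Office within 24 hours with a severity entry. A Clinical Coordinator independently determines its seriousness and causality (9.2.2), and a death also goes on the Death Form (10.1). Section 9.2.1.2 refers to SAE Form completion guidelines in the Investigator Site File, which are not at hand and may deal with unlisted events.

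A reader might also infer that a planned grade 4–5 rate is understated. No such rate is specified. It could appear in a statistical analysis plan, which was not available here, and that table might draw on SAE data.

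The consequence for treatment should not be overstated either. Section 7.4 withholds selumetinib for related intolerable events whatever their grade. Section 7.12 allows withdrawal for unacceptable toxicity, for unforeseen events and for an SAE that requires treatment to stop. For a fatal event the dose tables are moot. That a fallback 3 would be read in the grade 3 row is an inference, because the protocol is silent on the mapping.

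Finally, a three-level intensity scale can be defended as a design choice, since Appendix 3 separates severity from seriousness. The class of unlisted events may also be very small.

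Most of this stands, and it limits the point to recording and consistency. It does not remove the point. None of these routes corrects the AE Form grade, reconciles 9.2.1.1 with 9.2.1.2, or says which grade applies in 7.4.1 and 7.4.2. The separation of severity from seriousness does not help either, because 9.2.1.2 asks for severity on the CTCAE and 7.4 acts on CTCAE grade.

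**Conclusion.** The point holds in a narrow form. Followed exactly, 9.2.1.1 caps the recorded grade of an event outside the CTCAE at 3. It conflicts with 9.2.1.2 on the severity scale for the same serious event, and the capped scale has no stated relation to the grade-based rules in 7.4 to 7.4.2. A summary by grade taken from AE Form data would understate severity for these events by one or two levels.

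The expected effect is small. Events listed in the CTCAE are untouched, DLT counting is unaffected, and the serious events concerned remain visible as SAEs. The number of events involved cannot be derived from the protocol and is probably low. The conclusion rests on two assumptions: that at least some events fall outside the CTCAE, as 9.2.1.1 itself allows, and that the SAE completion guidelines do not already resolve the conflict. Low priority, but this is a stated site instruction that the protocol fixes badly, and correcting it costs almost nothing.

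**What to change.** - **Section 9.2.1.1:** extend the recording scale for events outside the CTCAE to five levels by adding (4) life-threatening and (5) fatal.
- **Section 9.2.1.2:** state that the same five-level scale is used on the SAE Form for these events, so that both forms carry one grade.
- **Sections 7.4, 7.4.1 and 7.4.2:** reconcile with the two sections above by stating how events outside the CTCAE are read in the dose-modification tables. Which action should follow is a clinical decision for the sponsor and investigators and is not proposed here.

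The recording change costs about one sentence in each of 9.2.1.1 and 9.2.1.2 and two extra codes on the forms. The reconciliation needs a short clarifying statement in 7.4. No visits, patients or assessments are added.
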